Consistent with the common conceptual model of EMR improving affective and functional recovery, this project has two co-primary outcomes, one of functional recovery, and one of affective recovery. Our primary measure of **functional outcome** is the **Barthel Index**, a 0-100 scale⁶³ that measures ability (time and physical assistance required) to perform 10 basic Activities of Daily Living or mobility items making it optimal for this highly debilitated population.^{62,64-66} The Barthel Index has excellent external validity: a higher score predicts greater likelihood of being able to live at home and degree of independence following discharge from the hospital.^{67,68} Secondary measures are gait speed (time to walk 6 meters, in meters/second) and 6 minute walk (number of feet walked in 6 minutes). These performance-based measures of physical function have found increasing favor as outcome measures in rehabilitation intervention studies, because of their strong external validity in predicting clinical outcomes such as hospitalization and mortality.^{3,69-71}

*The primary measure of **change in depression** is the Montgomery Asberg Depression*

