Explanation: The purpose of H1 is to examine the effectiveness of EMR. If H1 is supported, this could establish EMR as the gold-standard practice for post-acute rehabilitation. Our primary analysis is the change from baseline to Discharge. This single primary endpoint allows for an effectiveness test that is not confounded by length of stay differences or post-discharge issues beyond the reach of EMR.

2. Aim 2: Examine EMR's ability to overcome patient-level barriers to successful rehabilitation.

H2: The effectiveness of EMR for functional recovery will be greatest in: (a) patients with clinical depression; (b) patients with high levels of medical comorbidity; (c) patients with cognitive impairment.

Explanation: EMR was designed to overcome barriers to rehabilitation (for example, due to depression); therefore, the difference in functional recovery between EMR and SOC should be greater in the most vulnerable older adults. If H2 is supported, we will demonstrate that older adults with these common comorbidities benefit the most from high intensity, high engagement rehabilitation. If so, this would refute conventional wisdom in post-acute rehabilitation, codified in admission criteria for rehabilitation facilities, regarding the appropriate candidates for rehabilitation (as described in Significance).

3. Aim 3 (Secondary): Effect of EMR on MADRS scores on individuals with clinical depression.
4. Calculated a rate of clinical depression (SCID for those with elevated MADRS score):

22 participants had the SCID administered.

8 did not have depression diagnosis while 14 did have depression diagnosis.

Conclusion: only 14 individuals in the study had a clinical depression (ie, a diagnosis of depression). No further analyses to be done.

Additional Variables/Outcomes

6-Minute Walk/Gait Speed: Administered at Baseline and Discharge. Two components for 6-Minute Walk:

- 1) Distance Ambulated (feet): text box. If unable to complete, distance was entered as a 0.
- 2) Time: options are 6 minutes, Other time (MM:SS), and N/A

Two components for Gait Speed (Baseline, Day 30, Discharge):

- 1) Distance: radio button (10 meters, 4 meters, 0 meters). If unable, 0 meters selected.
- 2) Time (seconds): text box (if unable, time is 0).

Disposition (i.e., discharge to community vs. not)

Rehospitalization (rate).

Secondary analyses (not for main paper):

1. PANAS (A positive and a negative affect score).

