- b. Medical illness preventing study participation or accurate data collection (e.g., highly unstable cardiac illness such that early re-hospitalization is expected; metastatic or other cancer such that hospice is recommended or survival is limited).
- c. Moderate-severe dementia (demonstrated by chart diagnosis and/or short blessed score greater than 13).
- d. Progressive neurological condition such that recovery of function is not feasible.
- e. Patient did not have the ability to walk prior to hospitalization (e.g. paraplegic).
- f. Schizophrenia or other chronic or current psychotic disorder.
- g. Patient normally resides in a long-term care facility.

- iii. Recruitment: the numbers that will be presented in a CONSORT diagram include:
 - 1. # Screened/Consented and reasons for ineligibility.
 - 2. # Randomized to EMR vs SOC.
 - 3. # Present at each follow-up time point (i.e., Day 30, Discharge, Day 60, and Day 90); reasons for discontinuation/lost to follow-up.
 - 4. # Included in Final Analysis; reasons excluded from final analysis.
- iv. Withdrawal/follow-up

No follow-up was done for withdrawn participants. If a participant was withdrawn, then an attempt was made to obtain final prognosis information using clinical data available from the chart unless explicitly told not to do so by the participant.

v. Baseline Patient Characteristics

In addition to the screening variables described above, the variables below will also be summarized in a Baseline Characteristics Table. Continuous variables will be summarized using median and IQR while categorical variables will be summarized using counts and percentages. These statistics will be provided by condition (EMR Vs SOC) and as a whole.

- Barthel Index
- MADRS Score
- Gait Speed (Distance in meters and Time in seconds)
- 6-Minute Walk (Distance Ambulated, in feet)
- PANAS Score
- Short Blessed Test Score
- CIRS-G Score
- Clock Drawing Score

Analysis:

i. Outcome Definitions

- 1) Aim 1: Examine the effectiveness of EMR for improving functional outcomes in older adults admitted to SNFs for post-acute rehabilitation.

H1: EMR will improve functional recovery to a greater extent than standard-of-care rehabilitation.

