The secondary analyses for Six-Minute Walk distance and Gait Speed will use a Mann-Whitney U Test to test for differences in means between groups. In addition, a Chi-Square test will be employed to test for independence between condition and the secondary outcome variable re-hospitalization. Finally, the outcome of self-reported function will use a marginal model using time (30, 60, and 90 days), condition and time x condition as fixed effects, with a covariance structure specified based on BIC.

Exploratory analyses will also test whether the effects of age, gender, race and site (i.e., Barnes Jewish Extended Care Vs Alexian Brothers Sherbrooke Village) altered the conclusions of the primary results as well as the conclusions of the moderator results.

Note: we will not look at the nesting of subjects within therapists who are then nested within site as this is not possible due to the inconsistency of assigning therapists to participants.

iii. Missing Data

We use a marginal model which accounts for missing data (no multiple imputation was used).

iv. Harms

An adverse event (AE) is any untoward medical occurrence in a subject temporally associated with participation in the clinical study or with use of the experimental agent being studied. An adverse finding can include a sign, symptom, abnormal assessment (laboratory test value, vital signs, electrocardiogram finding, etc.), or any combination of these.

AEs will be labeled according to severity (i.e., mild, moderate or severe), which is based on the AE's impact on the participant.

AEs will be categorized according to the likelihood that they are related to the study intervention or other study procedures (i.e., definitely unrelated, definitely related, probably related, or possibly related).

SAEs that are unanticipated, serious, and possibly related to the study intervention will be reported to the IRB, and NIMH in accordance with requirements. Unexpected fatal or life-threatening AEs related to the intervention will be reported to the NIMH Program Officer within 7 days. Other serious and unexpected AEs related to the intervention will be reported to the NIMH Program Official within 15 days. Anticipated SAEs will be handled in a less urgent manner but will be reported to the IRB in accordance with their requirements.

v. Statistical Software

All analyses will be performed using SAS and/or R.

vi. References

none

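### As written, the SAP scores an unfinished six-minute walk as 0 feet, which conflicts with the protocol's definition and can reverse patients' ranks in the planned test

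*SAP*

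**What the plan says.** The SAP, under Additional Variables/Outcomes, records two components for the six-minute walk. The first is distance in feet, with the rule "If unable to complete, distance was entered as a 0". The second is a time field: "Time: options are 6 minutes, Other time (MM:SS), and N/A". The SAP does not define what counts as unable to complete. It also does not say what distance accompanies a time other than six minutes.

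Protocol C3 names the measure among the secondary functional outcomes: "Secondary measures are gait speed (time to walk 6 meters, in meters/second) and 6 minute walk". It specifies the walk as the number of feet covered in six minutes and contains no zero rule.

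For analysis, SAP Analysis Methods says: "The secondary analyses for Six-Minute Walk distance and Gait Speed will use a Mann-Whitney U Test". The baseline table in the SAP (Baseline Patient Characteristics) lists distance only. The time field appears in neither place.

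The gait-speed item in the same SAP section has its own zero code, worded slightly differently: "If unable, 0 meters selected".

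**The concern.** Under the protocol's definition, a patient who walks 300 feet and stops at four minutes has a result of 300 feet. Under the SAP's rule as written, the result is 0. That patient then has the same score as someone who could not take a step, and a lower score than someone who moved a few feet over the full six minutes.

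A rank test uses only the order of the values, so any reversal of order enters it directly. The distance measure becomes partly a measure of whether the test was completed. If early stopping is common, a real difference in walking distance could be diluted or missed, and the baseline median and IQR for the walk would be too low. The protocol calls the population highly debilitated, so early stops are foreseeable, and the form itself provides for them.

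**Working it through.** The SAP gives no power or other figure for the walk, so there is nothing of the plan's own to reproduce. The check has three steps.

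**1. The texts side by side.** The protocol sets no completion condition. The SAP's distance rule is triggered by not completing. The time field has three values: six minutes, another time in minutes and seconds, and not applicable. The second has an obvious use only for a walk that ended early. That leaves two readings:

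- Reading A (the rule as written): every early stop gets 0.
- Reading B (suggested by the time field): partial walks keep their distance, and 0 goes with not applicable.

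**2. Ranks for five hypothetical patients.**

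| Patient | Rank under A | Rank under B |
|---|---|---|
| Cannot start | 1.5 | 1 |
| 20 ft in 6:00 | 3 | 2 |
| 350 ft, stops at 4:30 | 1.5 | 4 |
| 300 ft in 6:00 | 4 | 3 |
| 600 ft in 6:00 | 5 | 5 |

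Under A the 350-foot walker ties with the non-starter and falls below the 20-foot walker. Under B there is no reversal.

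**3. Illustrative power of the Mann-Whitney test.**

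Inputs from the documents:
- 252 / 2 = 126 per arm (the protocol's planned total).
- d = 0.4 (Protocol G1 and SAP Sample Size). It was chosen there for the primary outcomes and is only borrowed here.
- Two-sided 5% (SAP Confidence Intervals and P-Values).

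Assumed inputs:
- The lowest 10% cannot start.
- The early-stop rates are those shown in the table.
- Stopping is either unrelated to walking capacity or correlated 0.5 with it.
- Every patient has a discharge walk.

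| Early stops | Distance kept | Zeroed, unrelated | Zeroed, correlation 0.5 |
|---|---|---|---|
| 10% | about 0.87 | about 0.73 | about 0.84 |
| 20% | about 0.85 (0.84 to 0.88) | about 0.55 (0.54 to 0.56) | about 0.78 (0.74 to 0.80) |
| 40% | about 0.87 | 0.25 to 0.27 | 0.59 to 0.62 |

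The ranges cover repeated runs and different details of how stopping is modelled. At 20% the loss is 0.85 − 0.55 = 0.30 if stopping is unrelated to capacity, and 0.85 − 0.78 = 0.07 at correlation 0.5. At 10% the losses are 0.87 − 0.73 = 0.14 and 0.87 − 0.84 = 0.03.

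A second model separates the effect of stopping from the effect of scoring. It takes means of 500 and 600 feet with SD 250 (100 / 250 = 0.4), a random 10% unable to start, and early stoppers who cover 40% to 90% of their distance. Stopping is unrelated to capacity. Power is 0.68 with no early stops. At 20% early stops it is 0.60 with distance kept and 0.35 with zeros. Stopping itself therefore costs 0.68 − 0.60 = 0.08, and the zero rule costs a further 0.60 − 0.35 = 0.25.

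**The case against.** The strongest reply is that the form points to reading B. A minutes-and-seconds option would serve little purpose if every early stop were overwritten with 0, and not applicable is the natural partner of a 0. The gait-speed item uses its zero code for patients who are unable, and unable to complete may mean no more than that. Under this reading the SAP and protocol agree, and no ranks are reversed.

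This reply stands as a limit on certainty. A reader might infer that patients were in fact mis-scored. The documents do not show that: they never report a 0 entered beside a stop time, and they do not say what the raters did. But the reply does not remove the point. The time field shows that a stop time could be recorded, not which distance was entered. The difference in wording between the two zero codes can equally mean a different trigger. The only distance rule on the page is the literal one, and nothing in the analysis corrects for it.

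A reader might also infer that EMR patients, pushed to work harder, would walk faster, tire sooner and be penalised by the zero rule. That is speculation. EMR changes how therapy sessions are run, the outcome ratings are made by a blinded rater, and neither document says anything about pacing during the test.

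It is also fair to say that the largest power losses assume stopping unrelated to walking capacity, which is the less plausible case in this population.

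**Conclusion.** The rule as written gives a wrong score to an early stopper, conflicts with the protocol's definition, and reverses ranks in the planned test. Whether it was applied that way is unknown. The SAP describes data entry in the past tense, so the answer lies in the records.

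The effect is confined to a secondary outcome and its baseline summary. The Barthel Index analysis and the moderator analyses under Aim 2 do not use the walk, so the point gives no reason to doubt the primary result.

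The size depends on an early-stop rate that the documents do not give. It ranges from negligible (10% stopping, correlation 0.5) to severe (40% stopping, unrelated to capacity). All these figures also assume 126 analysed per arm with no missing discharge walks and a borrowed d of 0.4. They show that the choice of reading can matter, and they are not estimates for this trial. The point should be settled before the walk is analysed.

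**What to change.** Restate the SAP rule: distance is the feet actually walked up to the recorded time, including when a time other than six minutes is selected. A distance of 0 is used only when the patient could not walk at all, with time recorded as not applicable.

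Before analysis:

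- List every baseline and discharge record with distance 0 and a time other than six minutes or not applicable.
- Correct these from the source form where a distance was written down.
- Run a stated sensitivity analysis for any that cannot be recovered.
- Report the number of early stops by arm.

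The cost is one sentence in the SAP and a short record check. If partial walks kept their distance all along, the check finds nothing and the sentence simply makes that explicit. The one real burden arises if walked distances were never written down, because those records then depend on the sensitivity analysis.

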Rating Scale, a commonly-used depression measure in clinical trials. We have used it in many prior studies of older adults. Our secondary measure is an 18-item positive and negative affect scale that measures positive and negative (depressed and anxious) affect. It measures the dominant dimensions of human emotional experience, which have important roles in both quality of life and as a predictor of success in geriatric rehabilitation. It is a combination of the full 10-item positive affect scale of the Positive and Negative Affect Schedule (PANAS),⁷⁷ plus five items from the brief PANAS measuring negative affect⁷⁸ and the three non-reverse coded items from a brief State Anxiety Scale⁷⁹ derived from the State Trait Anxiety Inventory to measure negative (anxious) affect. This scale uses participants' responses to questions (e.g., "how anxious do you feel at present") to assess their current feeling or affective states. The PANAS has excellent reliability in post-acute rehabilitation, where it is considered valuable in capturing the range of mood and motivational issues in this setting.⁸⁰ Our addition of specific anxiety items reflects the high rate of anxiety problems in post-acute rehabilitation.^{29,81-84} Additionally, this dimensional assessment of affect responds to calls by NIMH to use as outcomes dimensions that reflect more basic, validated emotional or behavioral states, as reflected in the Research Domain Criteria.⁸⁵ These depression/affect measures will only be carried out in participants with a baseline clinical diagnosis of current major or minor depressive episode, based on the Structured Clinical Interview for DSM-IV (SCID)⁸⁶ which we will carry out at baseline prior to randomization. We have considerable experience with the SCID in this population from prior NIMH-funded studies. Based on our pilot RCT experience, about 25% of eligible participants will have a current diagnosis; we will enrich the sample by continuing to recruit to ensure that 50% of randomized participants have a depression diagnosis, so that this study is adequately informative regarding benefits for late-life depression in this setting. Our test-retest Kappa (using different, blinded raters) for major/minor depression in this setting is 0.8 (good).

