2. PROMIS (Ability to Participate in Social Roles and Activities).
3. OARS IADL.

Process data: Measures of the dosage of intervention (# of EMR steps done in each therapy activity; PAT %; Rehab Participation Scale Score) before and after training.

Study Methods:

i. Trial Design:

This was a randomized, parallel-group trial where patients received either EMR or SOC therapy.

Patients who received EMR received therapy only from therapists who were trained and supervised in EMR. Their therapy sessions followed the EMR protocol. Otherwise, their SNF care did not differ from usual care.

Patients who received SOC received therapy only from PT/OTs (or assistants) who were not trained nor supervised in EMR. These therapists were monitored (videotaped or observed) but were not asked to do anything differently with their patients.

ii. Randomization:

Randomization (blocks...2 and 4 patients). was 1:1 to EMR or SOC with stratification by SNF site and by baseline depression status.

iii. Sample Size:

The sample size was based on 80% power to detect a Cohen's $d=0.4$ effect size on the ANCOVA difference in treatments at primary endpoint, based on a two-tailed $p<0.025$ (because two outcome measures are used). G*Power 3.1.2 was used for power calculations. A Cohen's $d=0.4$ is between "small" (0.2) and "medium" (0.5) effect sizes. Effect sizes for function were in the "large" range, $d=0.7-0.9$, but we acknowledge that these observed effect sizes are qualified by the small sample size, and it makes most sense to be more cautious regarding likely effect sizes in a full-scale study, hence our choice to power at $d=0.4$. Such an effect size is clinically relevant for the functional outcomes. *We will only examine affective recovery as an outcome for those who are "affectively impaired" to begin with; i.e., those with clinical depression at baseline; with this reduced N, we are powered at 80% for a $d=0.54$. This same power analysis would apply for any subgroup analysis of depressed; i.e., if we wish to demonstrate that EMR is effective both in the case of clinical depression and in "non-depressed" older adults.*

iv. Statistical Interim Analyses/Stopping Guidance:

Not applicable; we did not have any interim data analysis or early stopping plans.

v. Timing of Final Analysis:

All outcomes will be analyzed collectively.

vi. Timing of Outcome Assessments (including windows):

	Schedule of Assessments	SNF admit (baseline)	Day 7	Day 30	SNF discharg e	Day 60	Day 90

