Outcomes	Function						
	Barthel Index (primary outcome)	X		X	X	X	X
	Gait speed	X		X	X		
	6-minute walk	X			X		
	Depression SCID (given if indicated by MADRS)	X					
	MADRS	X		X			
	17-item positive and negative affect scale	X	X	X		X	X

Processes	Rehabilitation intensity					
	Patient active time & actigraphy (at 20% of sessions at random)	collected each session throughout stay				
	Treatment engagement					
	Observer-rated Rehabilitation Participation Scale (at 20% of sessions at random)	collected each session throughout stay				
	Fidelity data (at 20% of session at random)	collected each session throughout stay				
	Post-Treatment Affect					
	Self-Assessment Moniker (at 20% of session at random)	collected each session throughout stay				
	Patient Satisfaction and Treatment Fidelity Survey	Collected after therapy sessions				
	Other rehabilitation variables					
	Rehospitalization		X	X	X	X
	Disposition (home, long-term care)	X	X	X	X	X
	Social Participation (PROMIS Ability to Participate in Social Roles and Activities)				X	X
	Instrumental Activities of Daily Living (OARS IADL)				X	X
	Executive Functioning (Clock Drawing Test)	X				
	Fear of Falling	X				
	Readiness for Rehab	X	X			
	Short Blessed Test	X				
	Medical Comorbidity (CIRS-G)	X				
	Barthel Index: Pre-morbid version	X				

Statistical Principles:

i. Confidence Intervals and P-Values

Level of significance is 5%

ii. Adherence and protocol deviations

Protocol Deviation:

Any alteration or modification to the IRB-approved research without prospective IRB approval. The term research encompasses all IRB-approved materials and documents including the detailed protocol, IRB application, consent form, recruitment materials, questionnaires/data collection forms, and any other information relating to the research study.

Therapist adherence and competence was tracked two times per participant.

Variables: number of EMR principles used per therapy session; PAT.

iii. Analysis Populations

Trial Population:

- i. Screening data to describe representativeness of trial sample will include age, gender, race and ethnicity.
- ii. Eligibility

Inclusion Criteria:

- a. 65 years of age and older
- b. Admitted to a skilled nursing facility for post-acute care from PT and OT for 2 weeks or more.

Exclusion Criteria:

- a. Language, visual or hearing barriers to participation (e.g. unable to communicate with research staff).

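### The SAP's sample-size section keeps a power claim for depressed participants, and a two-outcome alpha, that other parts of the same SAP contradict

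*SAP*

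**What the plan says.** SAP, Study Methods iii (Sample Size), opens with "The sample size was based on 80% power to detect" a Cohen's d of 0.4, "based on a two-tailed $p<0.025$ (because two outcome measures are used"). It then turns to those with clinical depression at baseline and states, in the present tense, "with this reduced N, we are powered at 80% for a" d of 0.54. The next sentence applies the same calculation to any subgroup analysis of the depressed. The section gives neither a total N nor a number for the reduced N.

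The planning numbers are in the protocol. Its opening summary gives 252 participants. Section C3 names two co-primary outcomes, one functional and one affective, and says "we will enrich the sample by continuing to recruit to ensure that 50% of randomized participants have a depression diagnosis". Section G1 has the same power paragraph with the same 0.025.

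Other parts of the SAP differ from this:

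- Objectives, item 4: 22 participants had the SCID, 8 without and 14 with a diagnosis. It concludes that "only 14 individuals in the study had a clinical depression" and that no further analyses will follow.
- Objectives and the assessment schedule: function is the primary aim and the Barthel Index is the only outcome marked primary. MADRS in the depressed is a secondary aim.
- Statistical Principles i: "Level of significance is 5" per cent.

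**The concern.** Two statements in the sample-size section do not fit the trial that the rest of the SAP describes.

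First, a reader looking for the power available in depressed participants finds 80% at d = 0.54. Hypothesis H2(a), that benefit is greatest in clinical depression, is still in the plan, and the SAP states no other power figure for depression. A null result for H2(a) could therefore be taken as adequately powered.

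Second, the SAP carries two significance levels that could be applied to its one primary test. A Barthel p-value between 0.025 and 0.05 meets the 5% level but not the level on which the sample size was based. The SAP does not say which one governs, or why the two-outcome basis no longer applies.

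**Working it through.** **Inputs.** Planned N = 252 (protocol, opening summary). Planned depressed share 50% (protocol C3), so 0.5 × 252 = 126, or 63 per arm at 1:1. Two-sided alpha 0.025 (SAP, Sample Size) or 0.05 (SAP, Statistical Principles i). Effect sizes d = 0.4 and d = 0.54. Diagnosed participants: 14 (SAP, Objectives, item 4). The split by arm is not given; 7:7 is assumed, and it is the most favourable split.

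**Formulas** (n per arm, SD = 1 on the d scale).

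- Normal approximation: power = Φ(d√(n/2) − z), with z = 2.241 at 0.025 and 1.960 at 0.05.
- Detectable d at 80% power = (z + 0.842)√(2/n).
- The t versions use the noncentral t with 2n − 2 degrees of freedom and noncentrality d√(n/2).

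**Step 1: the plan's own figure for the depressed.** With n = 63 and alpha 0.025, 0.54 × √31.5 = 3.031, and Φ(3.031 − 2.241) = 78.5%. The t version gives 77.6%. Detectable d is 3.083 × √(2/63) = 0.549 (t: 0.555). So 80% at d = 0.54 is approximately what 126 depressed participants would give at 0.025. At 0.05 the power would be about 85 to 86%, so the stated figure belongs with 0.025.

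**Step 2: the same calculation with 14.** With n = 7, 0.54 × √3.5 = 1.010.

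| Two-sided alpha | Power for d = 0.54, normal | Power, t | Detectable d at 80%, normal | Detectable d, t |
|---|---|---|---|---|
| 0.025 | Φ(1.010 − 2.241) = 10.9% | 9.2% | 3.083 × √(2/7) = 1.65 | 1.85 |
| 0.05 | Φ(1.010 − 1.960) = 17.1% | 15.4% | 2.802 × √(2/7) = 1.50 | 1.63 |

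At this size the t figures are the ones to use. A less even split lowers power: at 4:10 it is 7.9% (0.025) or 13.4% (0.05), and detectable d is 2.04 or 1.81. The 14 participants are 14/126 = 11% of the number that the claim needs.

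**Step 3: the main comparison at each alpha, d = 0.4.**

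- At 0.025, 80% power needs 119 per arm, or 238 (t: 121 per arm, 242). The planned 252 gives Φ(0.4 × √63 − 2.241) = Φ(0.934) = 82.5% (t: 82.1%).
- At 0.05, 80% power needs 198 (t: 200). The planned 252 gives Φ(3.175 − 1.960) = 88.8% (t: 88.5%).

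These figures take no account of attrition or of clustering by therapist, and credit no gain from the baseline covariate.

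**The case against.** The strongest reply is that the section only records how N was chosen. It opens in the past tense, it repeats protocol G1, and Step 1 shows that the figure was sound to within about two points for the planned 126. That much stands: there was no miscalculation at the design stage. But the sentences on depressed participants are in the present and future tense. The paragraph was also revised for the SAP, since G1's day 21 became a reference to the primary endpoint, and the contradicted claims were left in.

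The second reply is that nothing depends on d = 0.54. This is largely right. The SAP drops the MADRS analysis in the depressed, and its Analysis Methods contain no such test and no depressed-subgroup contrast. A reader might infer that a null MADRS result would be misread, but no such result is planned. H2(a) is tested by entering MADRS as a continuous moderator in the primary model. The d = 0.54 calculation does not describe that interaction, and the SAP gives no power for it. What remains is that a reader could apply the figure to H2(a).

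The third reply is that 5% is the only testing level that the SAP states outright, and that 5% on one primary outcome is coherent. This also stands. A reader might infer an inflated type I error; testing two outcomes at 5% each would give 1 − 0.95² = 9.75% if they were independent, but the SAP does not plan two primary tests. A reader might also infer that alpha was relaxed after the results were seen. The only counts in the SAP are pooled baseline SCID results, with no outcome by arm, so the documents do not support that. They do not record the reason for the change either.

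**Conclusion.** The SAP contradicts itself on two points, and both should be corrected. The 80% power at d = 0.54, and its extension to any depressed subgroup, cannot hold with 14 diagnosed participants: power is about 9% at 0.025 or 15% at 0.05, and only effects of about d = 1.85 or 1.63 would be detected with 80% power. The 0.025 basis for two outcomes does not match a single primary outcome and a 5% level. It could change a conclusion only if the Barthel p-value fell between 0.025 and 0.05.

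This is a consistency defect. It does not show an error in the planned sample size, an inflated error rate or a data-driven change of threshold. The figures assume a 7:7 split of the 14, which the SAP does not report, and the protocol's planned 252, because the SAP states no N. They are two-sample comparisons, whereas the SAP's primary analysis is a marginal model.

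**What to change.** In SAP Study Methods iii:

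1. Label the calculation as the original design assumption.
2. Withdraw the d = 0.54 statement and its extension to depressed subgroups. Cross-refer to the 14 diagnosed participants in Objectives, item 4, and say that the d = 0.54 figure does not apply to the H2(a) test of continuous MADRS as a moderator.
3. State one two-sided alpha for the Barthel test. With one primary outcome this is 0.05, accompanied by a sentence recording that the affective co-primary was dropped on pooled baseline SCID counts without knowledge of outcomes by arm. If the sponsor cannot state that, keep the 0.025 of the protocol's power basis. Make Statistical Principles i agree.
4. Give the matching power for d = 0.4 at the number actually randomised. At the planned 252 it would be 82% at 0.025 or 88.5% at 0.05, by two-sample t, before attrition and clustering.

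The cost is wording only: no data collection or analysis changes. The plan loses its power claim for the depressed subgroup.
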